CBD has emerged as a possible intervention: We will address this need by conducting a study of CBD which has promise as an adjunctive treatment to MOUD. In humans, CBD administration has been shown to reduce attentional bias for tobacco-related cues in individuals with tobacco use disorder, as well as for cannabis-related cues among individuals who are regular cannabis smokers. CBD also significantly reduced cue-induced cravings compared to placebo in those with OUD but not taking MOUD^{9,10}. In both animal and human studies, CBD appears to target brain regions that mediate neural responses to drug-related cues, indicating the relevance of CBD in modulating the attentional and motivational saliency of drug-related cues, which contribute to the risk for relapse¹¹. In addition, CBD appears to attenuate the reactivity to stressors among individuals with social anxiety disorder. Stress-reactivity is another important driver of relapse risk among OUD patients. However, no human studies have been conducted in individuals with OUD to examine the impact of CBD on neurocognitive deficits including stress reactivity. Therefore, the critical question this study aims to answer is whether CBD can reduce cue- and stress-reactivity, reduce attentional bias to drug-related cues, and improve decision making in individuals with OUD.

2. Specific Aims and Objectives

To evaluate the impact of CBD on cue- and stress-reactivity, decision making, and attentional bias in individuals with OUD currently in treatment with medications for OUD (MOUD).

- Approach: In a double-blind, placebo-controlled, cross-over trial, reward-related neurocognitive processes will be assessed after administration of CBD 600mg or placebo
- Primary Outcome: The primary outcomes is cue-induced cravings (Opioid Craving Scale).
- Secondary Outcomes: The secondary outcomes are impulsive decision making (Iowa Gambling Task, Monetary Choice Questionnaire), attentional bias (Visual Probe Task), and physiologic and subjective stress-reactivity.
- Hypothesis: Individuals with OUD in MOUD treatment taking CBD will demonstrate less cue-induced cravings, stress-reactivity, poor decision making, delayed discounting, attentional bias and stress reactivity than those receiving placebo

3. General Description of Study Design

Overall study design: Double-blind, placebo-controlled, cross-over trial

Mass General Brigham

Research Consent Form

General Consent Form Template

Version Date: February 2021

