No benefits can be guaranteed from participation in the study. However, all enrolled participants will be receiving an adjunctive agent that is hypothesized to help reduce cue-induced cravings associated with their opioid use disorder, and it is possible that at least some subjects will experience a decrease in the severity of their cravings or stress-reactivity. An extensive screening procedure will ensure that individuals entering the trial will have no contraindications. Trained research personnel will perform all study procedures to minimize risks, discomforts, and adverse effects. Buprenorphine and methadone treatment are FDA-approved treatment for the treatment of OUD, and reduces illicit opioid use and related morbidities associated with OUD. This study will generate valuable information about the effect of combining cannabidiol with stable doses of buprenorphine or methadone for patients with OUD. The results will help inform the direction needed to take in developing effective strategies to improve the care of OUD patients taking medications. If successful, this line of research has the potential to significantly impact clinical practice of treating OUD by providing a viable medication adjunct to existing evidenced-based therapies.

9. Statistical Analysis

For all analyses, descriptive statistics will be used to summarize the data. All comparisons will utilize paired t-tests or non-parametric tests where appropriate. Alpha will be set at 0.05 for all analyses.

Primary outcome:

- Cue-reactivity: Cue-reactivity will be defined as the difference between baseline craving scores and the craving scores in response to opioid-related or neutral cues.

Secondary outcome:

- Subjective cravings: Craving scores will be rated on a 0 to 10 visual analog scale for each of the 3 items.
- Attentional bias: This is calculated as the difference in reaction time (RT) between when the probe replaced the neutral compared with the opioid-related images (i.e. RTneutral – RTopiod).
- Delayed discounting: Based on their responses to the MCQ, the rate of discounting, or k value, is calculated, which range from 0.00016 to 0.25. Higher values indicate greater discounting and impulsivity.

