- Impulsive decision making: A net score from the IGT is calculated by subtracting the number of disadvantageous selections from the number of advantageous selections (i.e. (C+D) - (A+B)), where negative scores indicate decision-making that favors immediate rewards despite negative consequences.

Research Consent Form

General Consent Form Template

Version Date: February 2021

Subject Identification

- Distress tolerance: This is measured as the length of time in number of seconds that participants engage in the third MTPT task.
- Subjective stress reactivity: Subjective stress reactivity will be calculated as the difference in the negative affect score from PANAS before and after the stressor task.
- Physiologic stress reactivity: Physiologic stress reactivity will be calculated as the difference in salivary cortisol levels and skin conductance before and after the stressor task.

Power analysis: The estimated mean change in cue-induced cravings scores from prior studies is -1.5 (SD 1.5). Based on this estimate, and a conservative estimate of a correlation of $r=0.60$ between the two time points, a sample size of 10 is needed for 88% power and two-tailed alpha set at 0.05 for a paired-samples t-test. A point estimate of the difference in the change and the 95% confidence interval will be reported. Conversely, if the change in cravings is not normally distributed, then a sum rank test will be used.

10. Monitoring and Quality Assurance

INSTRUCTIONS

Delete grey Instructions box upon completion of this section

Describe the plans that will be followed by study staff for monitoring and quality assurance, including:

- Adverse event criteria and reporting procedures
- Planned safety monitoring, e.g., data monitoring committee (DMC)/data and safety monitoring board (DSMB), independent monitor, PI-monitored, etc., including planned frequency of review. If DMC/DSMB monitored, include either charter as separate attachment or complete DMC/DSMB [APPENDIX](#)
- Outcomes monitoring, including planned frequency of review.
- Study stopping rules as applicable
- Internal monitoring of source data, protocol adherence, and recordkeeping, including which staff will be responsible and planned frequency of review
- Independent monitoring of source data as applicable

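### Every secondary outcome is tested at an unadjusted 0.05 and nothing limits what may be claimed from one; with no CBD effect, the chance of at least one p<0.05 is about 16% to 30%

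*Combined protocol and SAP*

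**What the plan says.** Section 9 (Statistical Analysis) sets one rule for significance: "Alpha will be set at 0.05 for all analyses". The tests are equally general: "All comparisons will utilize paired t-tests or non-parametric tests where appropriate".

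Section 9 names one primary outcome, cue-reactivity, and seven secondary outcomes: subjective cravings, attentional bias, delay discounting, the Iowa Gambling Task net score, distress tolerance, subjective stress reactivity and physiologic stress reactivity. Sections 2 and 6 give a shorter list of five: "The secondary outcomes are impulsive decision making (Iowa Gambling Task, Monetary Choice Questionnaire), attentional bias (Visual Probe Task), and physiologic and subjective stress-reactivity". Subjective cravings and distress tolerance are secondary only in Section 9, for example "Distress tolerance: This is measured as the length of time in number of seconds that participants engage in the third MTPT task".

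Section 2 has a single hypothesis, that patients taking CBD "will demonstrate less cue-induced cravings, stress-reactivity, poor decision making, delayed discounting, attentional bias and stress reactivity than those receiving placebo". The background just before it poses the study question jointly across reactivity, attentional bias and decision making.

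The power analysis concerns cue-induced craving only: "a sample size of 10 is needed for 88% power and two-tailed alpha set at 0.05 for a paired-samples t-test". The promise of a point estimate and 95% confidence interval stands in that same paragraph. No passage gives a testing order among secondaries, a condition that the primary succeed first, a multiplicity adjustment, or an exploratory label.

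**The concern.** For the secondaries, the only inferential standard in the plan is p<0.05, the same one that applies to the primary. Because the hypothesis covers most of them together with craving, the plan leaves room to report one significant secondary as support for that hypothesis even if craving shows nothing.

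With 10 participants this matters more than usual. A two-sided paired t-test on 10 pairs reaches p<0.05 only if the observed standardized difference exceeds 2.262/√10 = 0.72. Any chance finding will therefore look like a large effect. Section 8 (Benefits) says the results should guide further treatment development, so a false lead on a neurocognitive task could misdirect the next study.

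**Working it through.** **Inputs from the documents.** Alpha 0.05 for every test and paired t-tests (Section 9); two-sided testing and n=10 (power analysis, stated for the primary); seven secondaries (Section 9) or five (Sections 2 and 6).

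**Input not in the documents.** The correlation between different outcomes. The power analysis has "a conservative estimate of a correlation of $r=0.60$ between the two time points", but that links two measurements of one outcome and cannot be used here. Values of 0, 0.5 and 0.7 are assumed below, equal for all pairs of outcomes.

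**The plan's own figure first.** With mean change 1.5 in absolute size, SD 1.5 and r=0.60:
- SD of the paired difference = 1.5 × √(2 × (1 − 0.60)) = 1.342
- standardized effect = 1.5/1.342 = 1.118
- noncentrality = 1.118 × √10 = 3.54, with 9 degrees of freedom and critical t = 2.262
- power = 88.1%, against 88% stated. It reproduces.

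**Chance of at least one false-positive secondary, independent outcomes.** The formula is 1 − 0.95^k.
- k=7: 1 − 0.95^7 = 1 − 0.698 = 30.2%
- k=5: 1 − 0.95^5 = 1 − 0.774 = 22.6%

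**Correlated outcomes.** Simulation of 100,000 null trials per setting, 10 paired differences per outcome, each outcome tested by paired t at two-sided 0.05. For false positives favouring CBD only, each test contributes 0.025, so independence gives 1 − 0.975^7 = 16.2%; the correlated entries in that row are simulated.

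| Family | Independent | r=0.5 | r=0.7 |
|---|---|---|---|
| Seven secondaries (Section 9) | 30% | 24% | 19% |
| Five secondaries (Sections 2 and 6) | 23% | 19% | 16% |
| Seven, favouring CBD only | 16% | 12% | 10% |

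Even at an assumed correlation of 0.9, seven tests give about 12%. The rate stays well above 5% over the whole range examined.

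**The case against.** The best defence is that this is a 10-person, single-dose laboratory crossover with one named primary, one power calculation and every other outcome called secondary. Unadjusted secondary tests are acceptable in such a study if they are read as exploratory. Much of the defence on detail stands:

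- **The primary is protected.** A reader might infer that there is no hierarchy at all, or that the primary's error rate is inflated. The documents do not support that: a primary is designated in Sections 2, 6 and 9, and its test keeps its own 0.05.
- **No success rule is written for secondaries.** A reader might infer that the plan declares CBD effective on any significant secondary. No passage says so. The plan is silent, and the silence is the gap.
- **No single percentage is fixed.** It would be tempting to quote 24% as the error rate. That figure needs seven tests and a correlation of 0.5, which the documents do not give and which is hard to justify for measures as unlike as reaction times, card choices and cortisol.
- **The count is unsettled.** It is five or seven depending on the section, and it could be higher if components such as cortisol and skin conductance are tested separately.
- **The hypothesis is directional.** Only about half of the false positives would look like benefit.

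What does not stand is that the word secondary settles the matter. The protocol nowhere calls this trial a pilot or exploratory; in Section 7 the word pilot describes an earlier open-label study. The shared hypothesis in Section 2 also works against reading the secondaries as merely exploratory.

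**Conclusion.** The point holds as a gap in what may be claimed from secondary results, not as a fault in the primary test. If CBD has no effect on any secondary outcome, the plan gives about a 30% chance of at least one p<0.05 among seven independent secondaries, falling to 19% at a correlation of 0.7. For five secondaries the range is about 23% to 16%. Roughly half of each would favour CBD.

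These figures assume one two-sided paired t-test per listed outcome, all 10 participants contributing to each, and equal correlations between outcomes. The statement that the primary keeps its 0.05 assumes that it is analysed as one test. The change should be made: it is cheap and it alters what the trial can legitimately conclude.

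**What to change.** In Section 9, replace the sentence that sets alpha for all analyses with wording such as:

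> Cue-induced craving is the only confirmatory test, at two-sided 0.05. All secondary outcomes are exploratory. They will be reported as CBD–placebo differences with 95% confidence intervals, unadjusted for multiplicity, and no secondary result will be claimed as a demonstrated effect of CBD.

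Split the Section 2 hypothesis to match: one confirmatory hypothesis for cue-induced craving, and the remainder stated as exploratory.

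**Cost.** Text edits only, with no added participants, visits or data. The downside is that a lone secondary p<0.05 can no longer be claimed as a positive finding. The label restricts claims and leaves the percentages above unchanged, since an unadjusted 95% interval from the paired t-test excludes zero exactly when p<0.05.

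**Optional, only if the sponsor wants to claim a secondary.** Test the secondaries only after the primary is significant, using Holm at 0.05 over a list fixed in advance. Sections 2, 6 and 9 would first have to agree on that list. The price is power: with seven outcomes the strictest Holm step is 0.05/7 = 0.0071, where an effect as large as the one assumed for the primary (1.118 standardized) would have about 56% power, against 88% at 0.05.

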	Subject Identification
--	------------------------

Study schema: Shown below.

[figure not shown]
Research Consent Form

General Consent Form Template

Version Date: February 2021

Subject Identification

Study schema

Research Consent Form

General Consent Form Template

Version Date: February 2021

Subject Identification

4. Subject Selection

The proposed study is a double-blind, placebo-controlled, cross-over trial. The study will enroll 10 adult subjects with OUD currently receiving MOUD treatment with sublingual buprenorphine or methadone. Recruitment will occur from the outpatient programs that treat OUD patient at Brigham and Women's Hospital and Brigham and Women's Faulkner Hospital in Boston, MA, and at the Rutland Regional Medical Center in Rutland, Vermont.

Inclusion criteria:

- Age 18 to 65
- English speaking
- Receiving either buprenorphine or methadone for treatment of opioid use disorder for at least 3 consecutive months prior to enrollment
- Agreeable to abstaining from using any cannabis or CBD products for the duration of the trial.

Exclusion criteria:

- Any self-reported use of cannabis or CBD products in the past 30 days
- Current marijuana users
- Baseline depression (PHQ9) or anxiety (GAD7) scores of greater than 10
- Currently pregnant
- Hepatic liver enzymes greater than 3x upper normal limit
- Hypersensitivity to cannabinoids, sesame oil (CBD solution comes in sesame oil emulsion), or artificial strawberry flavoring.
- Currently taking any medications with known significant pharmacokinetic interactions with CBD

Subject recruitment procedures:

- We will use a variety of approaches to recruit for this study. We will use posted flyers at BWH clinical sites where OUD patients are being treated, and advertisements posted on Rally website. We will also utilize the Patient Gateway messages sent directly to active patients by sending an IRB-approved letter for recruitment. Potential participants will be identified by RPDR by searching for any MGB patient being treated with buprenorphine or methadone in their

Research Consent Form

General Consent Form Template

Version Date: February 2021

Subject Identification

medication list and also with a diagnosis of an opioid use disorder. In addition, research staff will approach clinical staff during the staff meetings.

- The RA will be largely responsible for identifying and recruiting potential participants.

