- Individuals will be recruited as soon as IRB approval is obtained and will continue until target sample size (n=10) is reached or when project period ends on December 31, 2022.
- Individuals will be recruited from the Boston area, and patients being treated for OUD at BWH affiliated clinical programs.
- OUD is present in about 3% of Massachusetts residents, and we have over 500 active OUD patients across BWH affiliated clinical programs with OUD and therefore should be able to reach recruitment target.
- At our clinical sites, Black and Latino patients are over-represented, and therefore our study will likely recruit an ethnically and racially diverse participant population.

5. Subject Enrollment

Adults with a DSM-5 diagnosis of OUD and who are currently in treatment with buprenorphine or methadone will be recruited. Patients with OUD at Brigham and Women's Hospital (BWH) and Brigham and Women's Faulkner (BWF) will be referred to study staff by their health care providers at these clinical sites for possible inclusion. Their health care providers, who will be known to the potential subject and will have first-hand knowledge of the patient's medical history, will (1) first give approval for his/her patient to be contacted/approached for research purposes, (2) initially introduce the study to the patient, and (3) obtain the patient's permission, verbally during the course of providing medical care, to be contacted by study staff. Subjects will also be recruited from the Partners Clinical Trials website, <http://Rally.partners.org>, as well as print advertisements and flyers posted at the clinics. Study visits will be conducted at the BWH Center for Clinical Investigation. Study staff will perform a preliminary screen on the telephone or virtually to establish suitability for the study. If suitable, a study staff will schedule the individual for a baseline visit which will be performed remotely or in-person. Informed consent will be obtained at the baseline visit in-person or remotely, after which the full inclusion and exclusion criteria will be applied. For remote consenting, study staff will utilize the Mass General Brigham REDCap eConsent. Those who meet criteria will then be randomized to either CBD first or placebo first, and scheduled for the two study visits.

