6. STUDY PROCEDURES

Overall approach: A total of 3 study visits are planned (**Table 1**) The first visit is the baseline visit, and the other two are double-blind placebo-controlled medication visits, where either CBD or placebo will be administered. Participants will be randomized using a random-number generator in a 1:1 ratio of CBD to placebo. During the baseline visit, after obtaining informed consent, participants will complete the baseline assessments. The subject will then be scheduled for their study visits 2 and 3 during which they will receive CBD or placebo in random order in double-blind fashion. Visits 2 and 3 will be scheduled at

Research Consent Form**General Consent Form Template****Version Date: February 2021**

Subject Identification

least 1 week apart to function as a washout. Baseline visit will take no longer than an hour, and the subsequent visits will take no more than 2 hours to complete.

Visit 1: Baseline

Participants will provide written informed consent, obtained by the PI or another study physician. The blood and urine samples collected during the Baseline Visit will be used for inclusion/exclusion purposes. Specifically, participants who are currently pregnant (as confirmed by the pregnancy test), or have hepatic liver enzymes greater than three times the upper normal limit (as confirmed by the liver function tests, or LFTs) will be excluded. Subjects will also complete baseline PHQ9, GAD7, BPI, TLFB, COWS, PANAS, and opioid cravings.

Visit 2: CBD or placebo

After arrival to the study site, the participant will receive either the CBD 600mg or placebo, immediately followed by obtaining baseline heart rate, blood pressure, PHQ9, GAD, BPI, TLFB, COWS, opioid cravings, and urine sample for toxicology testing. Heart rate and blood pressure will be monitored every 30 minutes (vital signs: heart rate, blood pressure) following receipt of CBD or placebo. At 60 minutes following the CBD or placebo administration, the participant will then proceed to complete the cue-reactivity test, visual probe task, Iowa gambling task, monetary choice questionnaire (MCQ), and the mirror tracing persistence task (MTPT). Just prior to and after the MTPT task, subjects will provide saliva sample and complete the positive and negative affect scale (PANAS). An additional saliva sample will be collected 20 minutes after the MTPT task.

Visit 3: CBD or placebo

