- Mirror Tracing Persistence Task (MTPT)^{17,18}: This task functions to elicit a stress response and measures distress tolerance. Participants are asked to trace a red dot along the lines of a geometric shape (e.g., star) using the computer's mouse, but the mouse moves the red dot in the reverse direction. Each time the participant moves the mouse out of the lines or hesitates for more than 2 seconds, a buzzer sounds, and the dot moves back to the beginning. Three progressively more difficult shapes are used. The first two rounds last 1 minute each. The third and final round tests for distress tolerance. Participants may terminate the task at any point during the third round by pressing on the space bar. In addition to measuring distress tolerance, prior studies have shown consistently that this method elicits a robust stress response in individuals with substance use disorders.
- Positive and Negative Affect Schedule (PANAS): Subjective stress reactivity will be measured using the Negative Affect subscale of the PANAS, a routinely used measure of both positive and negative emotions. This will be administered before and after stress induction with MTPT.
- Salivary cortisol: Hypothalamic-pituitary-adrenal (HPA)-axis response will be measured by collecting saliva for analysis of salivary cortisol before, immediately after, and 20-minutes after the stressor task.

Compensation: Participants will be reimbursed for travel/parking. In addition, subjects will be compensated \$100 for completing the baseline visit, \$50 for visit 2 and \$100 for completing visit 3 (\$250 total for completing all visits). We will utilize the Advarra payment systems to provide the study compensation.

Stopping rules: The Principal Investigator will assess all patients with regard to stopping criteria. This study will be stopped prior to its completion if: (1) the intervention is associated with adverse effects that call into question the safety of the intervention; (2) difficulty in study recruitment or retention will significantly impact the ability to evaluate the study endpoints; (3) any new information becomes available during the trial that necessitates stopping the trial; or (4) other situations occur that might warrant stopping the trial.

Research Consent Form

General Consent Form Template

Version Date: February 2021

Subject Identification

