Data sharing: Data collected will be shared by investigators at BWH as well as with investigators at Rutland Regional Medical Center using MGB Dropbox Business. Regarding sharing of data with the study sponsor, the principal investigator will be required to provide regular written progress reports. No identifiable information will be shared with the sponsor. Data collected at Rutland Regional Medical Center will only be kept for record-keeping requirements, and will not be used for future studies not described in this protocol. If the participant wished to withdraw their data from then we will withdraw the participant from the study as outlined in the protocol. Subjects who wish to withdrawal their data can ask the PI to do so. We are concurrently seeking IRB approval from Rutland Regional Medical Center.

7. Risks and Discomforts

The well-being of the study participants is of utmost importance. The in-depth screening procedure has been designed to ensure that individuals with any underlying medical or psychiatric illness are identified that may place them at greater risk for experiencing adverse effects during the study. The protocol raises several areas of concerns: confidentiality, emotional distress, adverse reactions to study procedures, suicidal ideation, and cannabidiol medication.

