APPENDIX A

Data Monitoring Committee / Data and Safety Monitoring Board Appendix

Research Consent Form

General Consent Form Template

Version Date: February 2021

Subject Identification

- *To be completed for studies monitored by Data Monitoring Committee (DMC) or Data and Safety Monitoring Board (DSMB) if a full DMC/DSMB charter is not available at the time of initial IRB review.*
- *DMC/DSMB Charter and/or Roster can be submitted to the IRB later via Amendment, though these are not required.*

A Data Monitoring Committee (DMC) or Data and Safety Monitoring Board (DSMB) will be convened for safety monitoring of this research study. The following characteristics describe the DMC/DSMB convened for this study (Check all that apply):

- The DMC/DSMB is independent from the study team and study sponsor.
- A process has been implemented to ensure absence of conflicts of interest by DMC/DSMB members.
- The DMC/DSMB has the authority to intervene on study progress in the event of safety concerns, e.g., to suspend or terminate a study if new safety concerns have been identified or need to be investigated.

- Describe number and types of (i.e., qualifications of) members:

The PI will serve as the data monitor given the small size of the study and low risk associated the use of a single dose of CBD. Given that this study will enroll a total of 10 subjects to receive a single dose of CBD 600mg or placebo, that study end points are not serious events (i.e. cue-reactivity), the risks associated with CBD is low, and that the study is completed rather quickly, the PI will serve as the data monitor. The PI will promptly report any adverse events to the IRB and the FDA where appropriate.

- Describe planned frequency of meetings:

Click or tap here to enter text.

- DMC/DSMB reports with no findings (i.e., “continue without modifications”) will be submitted to the IRB at the time of Continuing Review.
- DMC/DSMB reports with findings/modifications required will be submitted promptly (within 5 business days/7 calendar days of becoming aware) to the IRB as an Other Event.

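### Does enrolling exactly the 10 patients that the power calculation needs, with no allowance for loss, undermine the stated 88% power?

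*Combined protocol and SAP*

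**What the plan says.** The power analysis in Section 9 takes a mean change of -1.5 with SD 1.5 and a correlation of 0.60 between the two time points. It concludes that "a sample size of 10 is needed for 88% power and two-tailed alpha set at 0.05 for a paired-samples t-test". Section 9 makes every comparison a paired t-test or a non-parametric test, and promises a point estimate with a 95% confidence interval.

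Section 4 states: "The study will enroll 10 adult subjects with OUD currently receiving MOUD treatment". Its recruitment procedures add that recruitment "will continue until target sample size (n=10) is reached or when project period ends on December 31, 2022". Appendix A repeats the number: "Given that this study will enroll a total of 10 subjects to receive a single dose of CBD 600mg or placebo".

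Section 6 schedules Visits 2 and 3 at least one week apart, one with CBD and one with placebo, so a patient needs both to form a pair.

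The available text has no expected loss rate, no inflation of the sample, no replacement rule and no method for an incomplete pair. Loss is touched on in two places, both in Section 6. Under the stopping rules, the study may stop if "difficulty in study recruitment or retention will significantly impact the ability to evaluate the study endpoints". Under data sharing, "Subjects who wish to withdrawal their data can ask the PI to do so".

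**The concern.** The number required for analysis is also the number at which recruitment closes. Ten is the smallest number of complete pairs that reaches 88% on the plan's inputs, so any loss takes power below the quoted figure. If the 10 are counted at enrolment, recruitment could close before anyone knows whether 10 pairs exist.

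The order of events at baseline seems to make this worse. Section 5 says that "Informed consent will be obtained at the baseline visit in-person or remotely, after which the full inclusion and exclusion criteria will be applied", and Section 6 adds: "The blood and urine samples collected during the Baseline Visit will be used for inclusion/exclusion purposes". If consented patients counted towards the 10, exclusions for pregnancy or raised liver enzymes would use up places as well.

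At stake would be lower power for the primary outcome and a wider confidence interval. With 10 patients, each loss removes a tenth of the pairs.

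**Working it through.** **Inputs.** From Section 9: difference 1.5, SD 1.5 (read as the SD in each condition), correlation 0.60, two-sided alpha 0.05, paired t-test. From Section 4: n = 10. The documents give no loss rate, so the rates in the last table are assumptions.

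**Reproducing the 88%.** SD of the paired difference = 1.5 × √(2 × (1 − 0.60)) = 1.5 × √0.80 = 1.342. Standardised difference = 1.5 / 1.342 = 1.118. With 10 pairs the noncentrality is 1.118 × √10 = 3.54 on 9 degrees of freedom, and the noncentral t distribution gives 88.1%. The stated figure reproduces.

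**Fewer pairs, same inputs.** Power comes from the noncentral t with noncentrality 1.118 × √n and n − 1 degrees of freedom. The 95% half-width is t(0.975, n − 1) × 1.342 / √n.

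| Complete pairs | Power for 1.5 points | Difference with 88% power | 95% CI half-width |
|---|---|---|---|
| 10 | 88.1% | 1.497 | 0.960 |
| 9 | 83.5% | 1.605 | 1.031 |
| 8 | 77.4% | 1.740 | 1.122 |
| 7 | 69.5% | 1.917 | 1.241 |

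One loss costs 88.1 − 83.5 = 4.6 percentage points of power and widens the half-width by 1.031 − 0.960 = 0.07 points. Power falls below 80% at the second loss.

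**How likely are losses?** Suppose each of 10 patients is lost independently with probability q. Then P(no loss) = (1 − q)^10 and P(exactly one loss) = 10q(1 − q)^9.

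| Assumed q | Fewer than 10 pairs | 8 pairs or fewer | Average power |
|---|---|---|---|
| 5% | 40% | 9% | 85.6% |
| 10% | 65% | 26% | 82.8% |
| 15% | 80% | 46% | 79.6% |
| 20% | 89% | 62% | 75.9% |

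At 5% and 10%, most of the chance of a shortfall is the loss of a single pair: 40 − 9 = 31 of 40 points, and 65 − 26 = 39 of 65 points. The case becomes serious only at rates for which the documents offer no support.

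**Who counts towards the 10?** Appendix A describes the 10 as patients who receive study drug. Section 7 says that every subject in the trial gets a dose of CBD, and Section 8 says that all enrolled participants receive the agent. Read together, these make an enrolled patient a dosed patient, so someone excluded at baseline would not take one of the 10 places. The recruitment procedures in Section 4 use the term target sample size, close to the wording of the power analysis, which is compatible with counting completers. The verb enroll in Section 4 and Appendix A points the other way. The text does not settle it.

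**The case for a change.** The strongest opposing case is that 10 pairs is the exact minimum for 88%, that some loss is ordinary in a study with two treatment visits, and that prevention is cheap. Replacing non-completers would mean about 10 / 0.9 = 11.1 patients on average at 10% loss, from a pool that Section 4 puts at over 500. Enrolling 12 would give at least 10 pairs with probability 98% at 5% loss and 89% at 10%. The alternative reading, with 1.5 as the SD of the paired difference itself, leaves less room: exact power is 80.3% with 10 pairs and 74.8% with 9.

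The arithmetic stands, and so does the observation that the protocol is silent on replacement. The step from there to a required change does not. The 80.3% reading fails to reproduce the stated 88%, so it is probably not what was used. The stopping criterion and the right to withdraw data are general provisions and do not forecast attrition. Other features favour retention: treatment visits of at most two hours, at least three months on buprenorphine or methadone before entry, and a 100-dollar payment for completing Visit 3. Low cost makes a larger enrolment reasonable, but it does not show that the present number is a mistake.

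**Conclusion.** No change follows. The 88% is correct for the 10 patients the design enrols, provided that SD 1.5 is per condition and both visits are completed. The plan sets no minimum power, so 83.5% with 9 pairs breaks no commitment. The paired t-test and its confidence interval work in the same way with 9 or 8 pairs, as long as the losses are unrelated to the treatment difference, and replacing patients would not remove that assumption. The reported interval will show whatever precision was achieved.

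A material shortfall, with power below 80%, needs at least two lost pairs and also needs the 10 to be counted at enrolment. The documents establish neither. What remains is missing detail about what n = 10 counts and whether non-completers are replaced. A study team would ordinarily settle this during conduct and report the number of pairs analysed. Stating it would correct no figure and alter no analysis.
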